# 6. Heart Rate Variability (HRV) during information processing tasks (composite)

HRV, an index of parasympathetic reactivity, will be obtained during tasks (Mind in the Eyes, Global-local processing tasks) after mindfulness meditation alone and mindfulness meditation with TVS intervention. Increased HRV indicates increased parasympathetic reactivity, which suggests an increased physiological indicator of emotion regulation.

Analysis: Our canonical analysis strategy will be employed on HRV measured during the follow-up tasks

### 7. Galvanic skin response (GSR) during mindfulness meditation

GSR, index of sympathetic reactivity, will be obtained during mindfulness meditation alone and during mindfulness meditation with TVS intervention. Decreased GSR indicates decreased sympathetic reactivity, which suggests an increased physiological indicator of emotion regulation.

Analysis: Our canonical analysis strategy will be employed on GSR measured during the intervention

### 8. Galvanic skin response (GSR) during information processing tasks (composite)

GSR, index of sympathetic reactivity, will be obtained during tasks (Mind in the Eyes, Global-local processing tasks) after mindfulness meditation alone and mindfulness meditation with TVS intervention. Decreased GSR indicates decreased sympathetic reactivity, which suggests an increased physiological indicator of emotion regulation.

Analysis: Our canonical analysis strategy will be employed on GSR measured during the follow-up tasks

#### 9. Prefrontal gamma band EEG during mindfulness meditation

Prefrontal gamma band EEG will be obtained during mindfulness meditation alone and during mindfulness meditation with TVS intervention. Increased prefrontal gamma EEG band indicates increased physiological indicator of emotion regulation.

Analysis: Our canonical analysis strategy will be employed on EEG measured during the intervention

#### 10. Prefrontal theta band EEG during mindfulness meditation

Prefrontal theta band EEG will be obtained during mindfulness meditation alone and during mindfulness meditation with TVS intervention. Increased prefrontal gamma EEG band indicates increased physiological indicator of emotion regulation.

Analysis: Our canonical analysis strategy will be employed on EEG measured during the intervention

### **11.** Prefrontal gamma band EEG during information processing tasks (composite)

Prefrontal gamma band EEG will be obtained during tasks (Mind in the Eyes, Global-local processing tasks) after mindfulness meditation alone and mindfulness meditation with TVS intervention. Increased prefrontal gamma band EEG suggests an increased physiological indicator of emotion regulation.

Analysis: Our canonical analysis strategy will be employed on EEG measured during the follow-up tasks

# 12. Prefrontal theta band EEG during information processing tasks (composite)

Prefrontal theta band EEG will be obtained during tasks (Mind in the Eyes, Global-local processing tasks) after mindfulness meditation alone and mindfulness meditation with TVS intervention. Increased prefrontal gamma band EEG suggests an increased physiological indicator of emotion regulation.

Analysis: Our canonical analysis strategy will be employed on EEG measured during the follow-up tasks

# **13. Heightened state of awareness using 5-Dimensional Altered State of Consciousness questionnaire (5D-ASC)**

Participants will answer which experience (mindfulness alone or mindfulness with TVS) they found most profound, and answer the 5D-ASC based on the more profound experience. Higher scores on the 5D-ASC indicates increased heightening state of awareness. For each question, the score is on a likert scale (1 to 5).

Analysis: Our canonical analysis will be used with variables for prior altered state of awareness in the pre-intervention term.

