2.5 Self-report Measures

--Pre-task

- 1) Demographic and screening questionnaire
- 2) Mindfulness attention awareness scale (Carlson & Brown, 2005)
- 3) Patient Health Questionnaire (Kroenke, Spitzer, & Williams, 2001)
- 4) Meditation experience questionnaire
- 5) Drug history questionnaire (Ventegodt & Merrick, 2003)
- 6) modified Differential Emotion Scale (Fredrickson, Tugade, Waugh, & Larkin, 2003)

--During tasks

- 1) Positive and Negative Affect Schedule (Watson, Clark, & Tellegen, 1988) will be given initially, and then after each intervention (meditation vs. meditation + TVS). This will also be given after the completion of each task (Mind in the Eyes, Global Local Task)

--Post-tasks

- 1) 5-Dimensional Altered State of Consciousness rating scale(Dittrich, 1998)

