2.6 Tasks

OUTLINE of procedures during the tasks

--Calibration (EEG, Pupil/Eye tracking, baseline GSR/EKG, vibration)

--Intervention 1: Meditation*

--Tasks 1: Global-Local Test, Mind in the Eyes

--Intervention 2: Meditation and TVS*

--Tasks 2: Global-Local Test, Mind in the Eyes

*Participant will be randomized whether they get meditation first or meditation and TVS first

All of tasks will be video recorded (calibration, intervention, tasks). The videos may be reviewed by study personnel and investigators for quality assurance, training purposes, or analysis. Physical backups are kept in locked filing cabinets and are labeled with subject identification number and date only. Electronic video or audio files will be stored on a password protected server which only study personnel

can access. Video and audio recordings will be kept indefinitely and may later be reviewed by other researchers. Participants may request destruction of video or audio recordings, or may also request not to be audio or video taped.

Physiological measurements during tasks include galvanic skin response (GSR) measured using electrodes placed on the index and middle finger, pupillary dilation indices, EKG (electrocardiography) which will be measured using three electrodes (left clavicle, right clavicle, and under the right rib), respiration (using a respiration belt), and EEG (mobile EEG monitor on head) will be collected during: 1) calibrations, 2) interventions and 3) cognitive and affective tasks. All of the stated physiological measurements will be collected except pupillary dilation indices will not be collected during interventions (meditation, meditation + TVS) because participants are encouraged to relax and are given the opportunity to close their eyes during those times.

A) Calibrations:

Calibration tasks will initially be completed for physiology collection including a vibration calibration that allows assessment of individualized vibration frequency preferences, a GSR/EKG calibration at baseline, EEG calibration at baseline and pupillary dilation calibration. During the EEG calibration, there are some images that may evoke negative emotions, which is in the introduction, and participants are encouraged to stop the calibration at any time if they feel uncomfortable with the images.

B) Interventions:

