Participants will undergo 2 blocks (randomized for order). 1) guided mindfulness meditation and 2) guided mindfulness meditation with TVS (0.1 Hz to 100 Hz) using SubPac, which is a marketed, wearable vibration technology that can deliver TVS, worn like a backpack. Participants will be wearing the SubPac (vest with vibration) the whole time but only during mindfulness with meditation, will the vest vibrate at various frequencies. The intensity of stimuli can vary from barely detectable through somewhat uncomfortable, but will not be painful. Similar vibratory stimuli have been standardly used in [name]'s lab. The intensity of the vibration will be adjusted to the subjects' comfort. Each of the interventions will be have a 12 minuted guided mindfulness meditation, with or without vibration coming out of the vest. They are given the choice to either sit in a desk chair or in a lounge chair, both in the same room. We advise them to concentrate to the meditation and the feelings in their body.

C) Cognitive and affective tasks:

These tasks are standard for our emotion/cognitive research lab.

1. Global-local visual processing task (Fredrickson & Branigan, 2005)

-- In general, images contain both local and global features. This task determines which attention is first directed, either at the local features (details, parts) or global features (the whole)

-- There will be a letter "T" made up of 4 smaller letter "T's". The smaller T's and the large "T" are incongruent in its orientation. The global feature of the letter "T" (the whole) will be of a particular orientation (up, down, left, right) and the local features (details, parts, in this case the 4 smaller letter "T's") will be of a different orientation (up, down, left, right). Participants will have to choose an answer by looking at the letter "T". There is no right answer, and the participant has the choose between 1) a letter "T" with congruent 4 smaller "T's" in the orientation of the global features (the whole) or 2) A letter "T" with congruent 4 smaller "T's" in the orientation of the local features (details, parts).

2. Reading the Mind in the Eyes test (Baron-Cohen, Wheelwright, Hill, Raste, & Plumb, 2001)

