### **Canonical Analysis Strategy**

Our canonical strategy for all aims in which outcome measures (e.g., physiology) are examined preintervention and post-intervention will as follows:

**Quality Control:** Data will be inspected visually and using our lab's standard algorithms to eliminate subjects, blocks, and trials in which data do not appear to be representative of the obtained measure, e.g., for EEG, data are eliminated when >3 channels have outlying means, standard deviations, are interpolated, or have unacceptably high levels of impedance.

**Preprocessing:** Data will be preprocessed using our lab's standard procedures which are consistent with industry standard procedures, e.g., via guidelines for psychophysiology from the Society for Psychophysiological Research. Outliers will be rescaled via windsorization.

**Data Reduction:** if more than one outcome measure of a given type (e.g., electrodes, for EEG) are employed, principal components analysis (PCA) will be used to yield aggregate indices across proposed outcome variables.

**Analysis:** Pre-intervention index values will be interacted with intervention type (mindfulness alone vs. TVS added to mindfulness) to explain variance in post-intervention index values using hierarchical regression; in the absence of an interaction, preintervention values will be regressed from post-intervention values before using intervention type as an independent variable to explain variance in post-intervention values in a residual regression analysis. The change in R^2 will be used as an effect size. Type I error will be controlled across the number of examined factors. Each type of outcome listed separately below will be interpreted as a statistically separate family for control of familywise error.

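### Outcome 13 records one 5D-ASC score per participant, for the experience that participant chose, so the planned regression does not estimate the TVS effect, and the choice itself is not analysed

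*SAP*

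**What the plan says.** The protocol (2.6 Tasks) gives every participant both conditions in one session: "Participant will be randomized whether they get meditation first or meditation and TVS first". Section 2.5 lists the "5-Dimensional Altered State of Consciousness rating scale" once, under the post-task measures. The PANAS, by contrast, is scheduled there after each intervention.

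SAP outcome 13 has two steps. First, "Participants will answer which experience (mindfulness alone or mindfulness with TVS) they found most profound". Second, they "answer the 5D-ASC based on the more profound experience". The analysis reads: "Our canonical analysis will be used with variables for prior altered state of awareness in the pre-intervention term".

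The Canonical Analysis Strategy is written for cases where "outcome measures (e.g., physiology) are examined preintervention and post-intervention". Its model is: "Pre-intervention index values will be interacted with intervention type (mindfulness alone vs. TVS added to mindfulness". If there is no interaction, intervention type is tested as a main effect on the post-intervention value.

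Hypothesis 1.2 (Protocol 1.2) claims a more heightened state of awareness with TVS added than with mindfulness alone. Hypothesis 3.3 claims that TVS makes such states more likely, especially in people who have had them before. Outcome 13 is the only listed outcome for heightened awareness.

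**The concern.** With one score per person, intervention type in this regression can workably mean only the chosen condition. That is not randomised: it is a judgement made after both blocks, and it probably depends on the very scores being compared. The unchosen experience has no score, so no within-person contrast exists. Adjusting for prior altered states neither restores the missing score nor removes the selection.

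The regression may therefore shrink a real effect, show one where the means are equal, or reverse its sign. Which of these applies cannot be read from the data, because one score per person does not reveal how people choose. The moderation analyses (outcomes 14 to 16) cover all secondary outcomes and so inherit the problem. Meanwhile the forced choice, a direct comparison made by each participant under randomised order, has no planned analysis as an outcome.

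**Working it through.** **Possible codings of intervention type**

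- *By chosen condition.* This compares two self-selected groups of people, not two conditions.
- *By randomised order.* Both order groups contain both conditions. With no order effect the expected contrast is 0 whatever TVS does. In simulation at a true 0.50 SD effect, rejection stays near 5%.

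Neither estimates TVS against mindfulness alone. That conclusion needs no numbers.

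**How large could the error be?** The plan has no figure to reproduce, and every input here is assumed. Let A be the TVS score, normal with mean τ and SD sA. Let B be the mindfulness-alone score, normal with mean 0 and SD sB. Their correlation is r = 0.5 and sD is the SD of A − B. The participant chooses TVS when

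L = ρ(A − B)/sD + √(1 − ρ²)·e + c > 0,

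where e is independent standard normal noise. The link ρ says how closely choice follows the score difference (1 = fully), and c is any extra pull towards TVS, such as novelty. Write m = ρτ/sD + c. Then

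- mean score among TVS choosers = τ + ρ(sA² − r·sA·sB)/sD × φ(m)/Φ(m)
- mean score among mindfulness-alone choosers = ρ(sB² − r·sA·sB)/sD × φ(m)/Φ(−m)

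and the planned contrast is the first minus the second. Rejection rates are from 20,000 simulated trials per setting: N = 60, two-sided 5%, t-test by chosen condition, no prior-experience covariate unless stated.

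**1. True effect 0.50 SD, equal SDs, c = 0.** At ρ = 1: sD = 1, m = 0.5, φ = 0.352, Φ = 0.691. The means are 0.5 + 0.5 × 0.352/0.691 = 0.755 and 0.5 × 0.352/0.309 = 0.570, so the contrast is 0.184.

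| Link ρ | Contrast (true 0.50) | Power, planned |
|---|---|---|
| 1 | 0.18 | 10% |
| 0.7 | 0.34 | 25% |
| 0.5 | 0.42 | 36% |
| 0.3 | 0.47 | 42% |

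A paired comparison of two scores per person has 97% power. At N = 40 and N = 100 the planned power at ρ = 1 is 8% and 15%, against 87% and 99.8% paired.

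**2. No mean effect, unequal SDs, c = 0.** With sA = 1.5, sB = 1 and ρ = 1: sD = √(2.25 + 1 − 1.5) = 1.323 and φ(0)/Φ(0) = 0.798. The means are 1.5/1.323 × 0.798 = 0.905 and 0.25/1.323 × 0.798 = 0.151, so the contrast is +0.75 where the truth is 0.

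| TVS SD (alone = 1) | Contrast, ρ = 1 / 0.5 | Rejects, ρ = 1 / 0.5 |
|---|---|---|
| 0.8 | −0.31 / −0.16 | 31% / 10% |
| 1.1 | +0.16 / +0.08 | 9% / 6% |
| 1.2 | +0.32 / +0.16 | 22% / 9% |
| 1.5 | +0.75 / +0.38 | 74% / 21% |

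A covariate correlated 0.3 or 0.5 with both scores lowers the 1.5 case only to +0.69 or +0.58 at ρ = 1 (rejecting in 70% or 63%).

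**3. Novelty: 75% would choose TVS with no effect at all (c = 0.674); true effect +0.20 SD, equal SDs.** At ρ = 1: m = 0.874, φ = 0.272, Φ = 0.809. The means are 0.2 + 0.5 × 0.272/0.809 = 0.368 and 0.5 × 0.272/0.191 = 0.713, so the contrast is −0.345. At ρ = 0.7, 0.5 and 0.3 it is −0.16, −0.04 and +0.06. With r = 0.7 instead, the four values are −0.25, −0.09, +0.01 and +0.09. With r = 0.3 the value at ρ = 1 is −0.42.

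In the settings of cases 1 and 3 that were checked, the covariate moved the contrast by no more than 0.003.

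**When the plan does no harm.** With equal SDs, no effect and no novelty shift, the contrast is unbiased and the test keeps its 5% level.

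**The case against.** The strongest reply is that the numbers depend on how the case is chosen. A 74% false-positive rate needs both a 1.5-fold SD and a choice fully determined by the score. With a TVS SD of 1.1 it is 9% or less. The sign reversal at ρ = 0.5 disappears if the within-person correlation is 0.7. At ρ = 0.3 a contrast of 0.47 against a true 0.50 is nearly right, and the power gap there is mostly the loss from having one unpaired score. All of this is correct. It limits what can be said about size, but it does not turn the planned contrast into an estimate of the TVS effect.

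It is also fair that outcome 13 adapts the pre/post strategy by placing prior altered-state variables in the pre-intervention term, so the absence of a baseline 5D-ASC adds nothing to the selection problem. The lack of a named instrument for that term is only a query, since the meditation-experience or drug-history questionnaires may contain suitable items.

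On the remedy, two objections stand in part. Side-by-side retrospective ratings may carry the same novelty preference as the choice. And Hypothesis 3.3 speaks of likelihood, while a mean difference is a related but different quantity.

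**Conclusion.** The concern holds. As written, outcome 13 cannot answer Hypothesis 1.2 or the TVS comparison in Hypothesis 3.3, and the forced choice goes unanalysed. This follows from the text alone: one self-selected score per person, both conditions given to everyone, and a regression on intervention type.

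The size is unknown because the documents give no SD, correlation, choice mechanism or N. Under the assumptions shown, a true 0.50 SD effect appears as 0.18 to 0.47 SD. Equal means can give a spurious contrast in either direction (−0.31 to +0.75), and a true +0.20 SD can appear as negative. This should be fixed before analysis. It concerns a secondary outcome and leaves both primary outcomes untouched.

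**What to change.** **Preferred.** Have each participant complete the 5D-ASC for each experience, both after the final task. Suggested SAP wording:

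> Outcome 13 is the within-participant difference in 5D-ASC score (TVS minus mindfulness alone), regressed on randomised order coded −0.5/+0.5. The intercept, the unweighted mean of the two order groups, is the TVS effect. For Hypothesis 3.3, prior altered-state experience, measured by [named item or questionnaire] and mean-centred, is added as a predictor of this difference.

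The order term should not be mean-centred. With a pure order effect of −/+0.5, no TVS effect and groups of 35 and 25, the intercept would then be (35 × (−0.5) + 25 × 0.5)/60 = −0.08 instead of 0. The SAP must name the prior-experience instrument, and should say that it models a score difference where Hypothesis 3.3 refers to likelihood.

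*Cost.* One more questionnaire in a session of up to 4 hours (Protocol 2.2) in which incomplete data are already expected (Protocol 2.7). The 97% power assumes that retrospective ratings behave like the modelled scores. The estimate also assumes no differential carryover: if TVS given first raised the later mindfulness-alone score by 0.2 SD, the bias is −0.2/2, and a true 0.50 would be estimated as 0.40.

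**Fallback, if a second rating is not accepted.**

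> The choice of the more profound experience, coded as first or second block, is compared between the two randomised order groups by the Mainland-Gart test. It tests which experience felt more profound, not the difference in 5D-ASC score. The single 5D-ASC score is reported descriptively, with no between-condition test.

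*Cost.* SAP wording only, since the choice is already collected, but it answers a different question. At 30 per order group and a true 0.50 SD effect, its exact power is 80%, 47%, 25% and 10% at ρ = 1, 0.7, 0.5 and 0.3, so at weak links it is below the planned test. In the novelty case with no 5D-ASC effect (ρ = 0.7) it rejects in 97%, against about 17% for the planned contrast. It must therefore be read as a test of preference only.

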### Other Pre-specified Outcome Measures: Moderation Analyses

#### **Canonical Moderation Analysis Strategy**

Moderation analyses will be analyzed by adding a third and fourth level to the hierarchical regressions described in our Canonical Analysis Strategy. On the third level, moderating variables are added. On the fourth level interactions of the moderating variables with primary and secondary outcome variables will be added. The change in R^2 from the third to the fourth level will be used as an effect size, and the significance of adding the interaction term on the fourth step will be interpreted as the significance of the moderation effect. Statistically significant moderation effects will be followed with creation of level curves for the 25th, 50th, and 75th percentiles for relevant variables to understand simple effects of the moderator on primary and secondary outcomes.

#### 14. Moderation of primary and secondary outcomes by Trait mindfulness using Mindful Attention Awareness Scale (MAAS)

MAAS will be given at the beginning of the study. It is a 15-item scale designed to assess a core characteristic of mindfulness. Score is 1-6 (average from 1-6 for 15 items). High scores is correlated with increased mindfulness. MAAS may be a predictor of objective and subjective primary and secondary outcome measures

Analysis: Our canonical moderation analysis will be used with variables for group and trait mindfulness in the pre-intervention term.

## **15. Moderation of primary and secondary outcomes by modified Differential Emotions Scale (mDES)**

For this scale, emotions scores are created by computing the mean of 10 positive and 10 negative emotions respectively. (0-4 for negative, 0-4 for positive). These scores may may be a predictor of objective and subjective primary and secondary outcome measures

Analysis: Our canonical moderation analysis will be used with variables for trait positive affect and subjective stimulus rating measures in the pre-intervention term

#### 16. Moderation of primary and secondary outcomes by Meditation Frequency Questionnaire (whether they meditate, and weeks/hours of meditation per week)

The questionnaire, which we have created, asks whether the participant meditates and how many minutes/hours a week do they meditate. The number of minutes/hours per week of meditation may be a predictor of objective and subjective primary and secondary outcome measures.

Analysis: Our canonical moderation analysis will be used with variables for meditation frequency and subjective stimulus rating measures in the pre-intervention term
